11.0 Study Timelines

11.1 Describe the anticipated duration needed to enroll all study subjects.

Response: It is anticipated it will take 3 years to enroll all study subjects.

11.2 Describe the duration of an individual subject's participation in the study. Include length of study visits, and overall study follow-up time.

Response:

Prior to participation, subject will complete a five minute screening over the phone or through an online questionnaire. Subjects that pass the initial screening will complete three further screening sessions lasting 45 minutes each and three dietary recalls, lasting 15 minutes each. Eligible participants will then attend one

laboratory visit for the IT-HOME, lasting about 45 minutes, and 45 minute intervention sessions once a week for 37 weeks. In addition, subjects will complete 3 dietary recalls over the phone, each lasting 15 minutes, and three laboratory sessions to collect anthropometrics, FRR, and parental reinforcing value of food, lasting about 45 minutes, at 3-m, 6-m, 12-m, and 24-m, and IT-HOME, lasting about 45 minutes, at 6-m, 12-m, and 24-m. During the second year, subjects will attend twelve 45-minute intervention sessions, one per month, for the maintenance phase. Between the ages of 2-4 years of age, you will attend three laboratory sessions which will last about 45 minutes long each, with 3 dietary recalls lasting about 15 minutes each. This is a total of 55.5 hours per subject over 2 years with the additional time at 2-4 years of age.

At home height/weight measurements due to COVID-19 should take approximately 30 minutes. Validation checks during in-lab follow up appointments should take approximately 15 minutes.

11.3 Describe the estimated duration for the investigators to complete this study (i.e. all data is collected and all analyses have been completed).

Response:

It is estimated to take approximately 5 years to complete the study (see above table). We propose to complete our randomized trial in 4 cohorts (Cohort 1: n = 20; Cohort 2: n = 24; Cohort 3: n = 24; Cohort 4: n = 24). Months 0-3 will provide time for IRB approval, protocol development, and staff training; months 3-6 for subject recruitment and baseline data collection of Cohort 1. We propose completing the one year intensive phase of Cohort 1 families by month 18, and the maintenance phase by month 30. During months 12 – 15 we will initiate recruitment and baseline measurements of Cohort 2, and the intensive and maintenance phases will be done by month 36. During months 18 – 21 we will initiate recruitment and baseline measurements for Cohort 3, and the intensive and maintenance phases will be done by month 45. The same fashion of subject recruitment and data collection timeframe will be followed by families of Cohort 4. All data collection is expected to finish by month 54. We will complete data entry and data analysis, generate new grant preparation based on ideas developed in the funding period, and compile manuscripts for publication and follow up grants during months 48 – 60.

12.0 Setting

12.1 Describe all facilities/sites where you will be conducting research procedures. Include a description of the security and privacy of the facilities (e.g. locked facility, limited access, privacy barriers). Facility, department, and type of room are relevant. Do not abbreviate facility names.

NOTE: Examples of acceptable response may be: "A classroom setting in the Department of Psychology equipped with a computer with relevant survey

administration software,” “The angiogram suite at Buffalo General Medical Center, a fully accredited tertiary care institution within New York State with badge access,” or, “Community Center meeting hall.”

Response:

The research, including will be conducted in the Behavioral Medicine Laboratory located in G56, G58, G90. Each laboratory room is equipped with computers and is child-friendly with age-appropriate toys, rugs, and wall-hangings. The Music Together® Intervention will take place in Betty’s Music Studio. The play date intervention will take place in one of the lab rooms at the Behavioral Medicine Laboratory.

12.2 For research conducted outside of UB and its affiliates, describe:

- *Site-specific regulations or customs affecting the research*
- *Local scientific and ethical review structure*

NOTE: This question is referring to UB affiliated research taking place outside UB, i.e. research conducted in the community, school-based research, international research, etc. It is not referring to multi-site research. UB affiliated institutions include Kaleida Health, ECMC, and Roswell Park Cancer Institute.

Response:

N/A: This study is not conducted outside of UB or its affiliates.

13.0 Community-Based Participatory Research

13.1 Describe involvement of the community in the design and conduct of the research.

NOTE: Community-Based Participatory Research (CBPR) is a collaborative approach to research that equitably involves all partners in the research process and recognizes the unique strengths that each brings. CBPR begins with a research topic of importance to the community, has the aim of combining knowledge with action and achieving social change to improve health outcomes and eliminate health disparities.

Response:

N/A: This study does not utilize CBPR.

13.2 Describe the composition and involvement of a community advisory board.

Response:

N/A: This study does not have a community advisory board.

14.0 Resources and Qualifications

*14.1 Describe the qualifications (e.g., education, training, experience, expertise, or certifications) of the Principal Investigator **and** staff to perform the research. When applicable describe their knowledge of the local study sites, culture, and society. Provide enough information to convince the IRB that you have qualified staff for the proposed research.*

NOTE: If you specify a person by name, a change to that person will require prior approval by the IRB. If you specify a person by role (e.g., coordinator, research assistant, co-investigator, or pharmacist), a change to that person will not usually require prior approval by the IRB, provided that the person meets the qualifications described to fulfill their roles.

Response:

The Principal Investigator is an expert on applying basic behavioral science paradigms to ingestive behavior, including research on food reinforcement. The Principal Investigator has published a variety of empirical and theoretical papers and has experience in administration and coordination of studies.

The Co-Investigators have extensive experience conducting human studies in the field of maternal health and nutrition, food reinforcement, and/or caregiver-infant observational and interview protocols.

The data manager/statistician has the training, ability, expertise, and experience in exercise science, clinical trials, and/or longitudinal trials. The data manager/statistician has experience with traditional statistical methods, as well as more sophisticated methods such as Mixed-Effect Regression Models, resampling techniques, and/or intention to treat approaches of longitudinal data.

The project coordinator will have experience conducting human research, scheduling test sessions, IRB submissions, and overseeing staff.

The research support specialists will have experience implementing study protocols and procedures.

The play date leader will have experience in child-care and child-safety.

The coders of observational assessment will have experience conducting observational studies.

The programmer will have a background in social media and recruitment, as well as the ability to manage the components of ecological momentary intervention.

Describe other resources available to conduct the research.

14.2 Describe the time and effort that the Principal Investigator and research staff will devote to conducting and completing the research.

NOTE: Examples include the percentage of Full Time Equivalents (FTE), hours per week. The question will elicit whether there are appropriate resources to conduct the research.

Response:

Principal Investigator: will have an appointment of 2.0 FTE
Co-Investigators: will have an appointment of .40 FTE
Data Manager/Statistician: .25 FTE for years 01-03 and .50 FTE for years 04-05.
Project Coordinator: 1.0 FTE
Research Support Specialists: 1.0 FTE in years 01-03, .5 FTE in year 04, and .25 FTE in year 05.
Play Date Leader: .50 FTE for years 01-03, .25 FTE for year 04, and .05 for year 05.
Coders of Observational Assessment: .50 FTE for years 01-04, and .05 FTE for year 05.
Programmer: .25 FTE for all 5 years

14.3 Describe the availability of medical or psychological resources that subjects might need as a result of anticipated consequences of the human research, if applicable.

NOTE: One example includes: on-call availability of a counselor or psychologist for a study that screens subjects for depression.

Response:

There are minimal potential physical, psychological, social, legal, or other risks. As such, there are no medical or psychological resources available to participants.

14.4 Describe your process to ensure that all persons assisting with the research are adequately informed about the protocol, the research procedures, and their duties and functions.

Response:

All personnel working on the project are required to complete the CITI training as required by IRB. Additionally, there are extensive procedures manuals that are read and followed by all personnel. The Project Coordinator is responsible for training all staff on data collection and recording procedures.

15.0 Other Approvals

15.1 Describe any approvals that will be obtained prior to commencing the research (e.g., school, external site, funding agency, laboratory, radiation safety, or biosafety).

Response:

Approval will be obtained from our funding agency, NIH.

N/A: This study does not require any other approvals.

16.0 Provisions to Protect the Privacy Interests of Subjects

16.1 *Describe how you will protect subjects' privacy interests during the course of this research.*

NOTE: Privacy refers to an individual's right to control access to him or herself. Privacy applies to the person. Confidentiality refers to how data collected about individuals for the research will be protected by the researcher from release. Confidentiality applies to the data.

Examples of appropriate responses include: "participant only meets with a study coordinator in a classroom setting where no one can overhear", or "the participant is reminded that they are free to refuse to answer any questions that they do not feel comfortable answering."

Response:

The recruitment procedures described in this protocol make use of posted flyers, and web posting. Participants may call the laboratory, of their own free will, and thus are controlling access to their privacy. The participant is reminded that they are free to refuse to answer any questions they do not feel comfortable answering.

16.2 *Indicate how the research team is permitted to access any sources of information about the subjects.*

*NOTE: Examples of appropriate responses include: school permission for review of records, consent of the subject, HIPAA waiver. This question **does apply** to records reviews.*

Response:

17.0 If subjects are unable to come to the south campus and unable to have us visit them at home, the research team will be permitted to contact the child's Pediatrician to obtain an up-to-date height/weight.

18.0 Data Management and Analysis

18.1 *Describe the data analysis plan, including any statistical procedures. This section applies to both quantitative and qualitative analysis.*

Response:

Descriptive statistics will be determined, and the distribution of each variable will be examined to assess normality. Appropriate transformations based on the distribution will be considered prior to analysis. Mixed model analysis of covariance (ANCOVA) will be used to examine the changes in the motivation to eat versus motivation to engage in alternative behaviors (FRR), infant daily energy intake, zWFL and home environment between the music and control groups. All analyses will be intention to treat, and will include all families that are randomized. The primary outcomes will be analyzed using SAS PROC MIXED (mixed ANCOVA), which will include random intercepts and time effects clustered within participants, adjusting for any family, parental, and infant temperament confounders that are different between the groups. Mixed ANCOVA accounts for repeated observations over time of participants,

and allows analysis with missing data. The models examine group (music or control), time in months (0, 3, 6, etc.) and their interaction as class variables and planned comparisons will be done assessing group differences to specific measurement interval after randomization (3, 6, 12, and 24 months). FRR, daily energy intake, zWFL, and home environment enrichment score are expected to be different between groups from baseline through the 2-year study. We predict that the relative reinforcing value of music will increase as the program is extended from 6 weeks to one year, and the reinforcing value of food will decrease during the year of intervention. Since the intervention is designed to enrich the home environment to support greater involvement in music, we expect the increased reinforcing value of music and the decreased reinforcing value of food to be maintained during maintenance period. In addition, we predict infants in the music group will show less weight for length gain over time compared to the control group at 12 and 24-month assessments. All analysis will be computed using SYSTAT and SAS .

18.2 If applicable, provide a power analysis.

NOTE: This may not apply to certain types of studies, including chart/records reviews, survey studies, or observational studies. This question is asked to elicit whether the investigator has an adequate sample size to achieve the study objectives and justify a conclusion.

Response:

The sample size for this proposal is based on the effect size of our pilot randomized controlled trial of an enriched music experience versus play dates on reducing relative food reinforcement and standardized weight for length in 9-15-month-old infants who were high in food reinforcement. Between groups differences in FRR showed an effect size (ESd) of 0.978. To detect differences for an ESd = 0.978 between the music and control groups with power at 0.80 and alpha at 0.05, 18 subjects per group are needed. The effects for standardized weight for length showed an ESd of 0.712 in zWFL differences between groups. Differences this large with power at 0.80 and alpha at 0.05 can be observed with 32 subjects per group. To be conservative, we will use a lower ESd = 0.667 for differences in infant weight (zWFL) change between groups. At power at 0.8 and alpha at 0.05, 37 subjects per group are needed. To control for attrition, we will recruit an additional 25% of parent-infant dyads at baseline, which will bring our total amount to be 46 subjects per group, or 92 subjects total. We feel as if this is a conservative estimate of treatment effects since this is a smaller effect size than we observed at six weeks in the pilot study, and we realistically think that the effects will be greater after a year of intervention.

18.3 Describe any procedures that will be used for quality control of collected data.

Response:

The primary investigator will be responsible for monitoring data safety at the weekly meetings. This includes ensuring confidentiality procedures are being followed in both recruitment and data collection. The types of data that will be monitored include demographic information and responses to questionnaires and assessments. The primary investigator will also be responsible for reporting serious events that occur during the laboratory sessions to the SBSIRB within 48 hours. The only anticipated serious event would be an allergic reaction to a food, previously unknown to the participant

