shown reduced access to cognitive enhancement activities at home between the ages of 0-8 years is associated with a greater than twofold increased risk of becoming obese six years later (Strauss & Knight, 1999). It has long been known in basic animal research that providing stimulating environments is protective against the development of drug self-administration (Cosgrove, Hunter, & Carroll, 2002), also consistent with the hypothesis that providing stimulating alternatives to food may be protective against the development of obesity.

We recently conducted a pilot study to test whether strengthening alternatives to eating can shift the balance of the motivation to eat or engage in alternative behaviors. The motivation to eat or engage in alternative behaviors was operationalized by the relative reinforcing value of food versus alternative behaviors, a well-validated approach in behavioral economics. Twenty-seven infants with high motivation to eat were randomized to music engagement versus attention play date control. Results showed a reduction in food reinforcement and a reduction in reinforcing value of food versus alternatives to eating after the treatment (Kong, Eiden, et al., 2015).

The proposed study extends this research in a larger sample of infants studied over a two year period to provide a better test of the short and long-term efficacy of this intervention approach on obesity-related outcomes. We propose a randomized, controlled trial to assess the effects of a 24-month music enhancement program versus an attention placebo play date in 92 9-15-month-old healthy infants who are strongly motivated to eat versus engage in other behaviors. The 12 month intervention includes 4 semesters of intervention (Winter, Spring, Summer, and Fall), comprised of 37 once per week group meetings of 10-12 infant-parent dyads. A 12-month maintenance phase with monthly meetings will be followed after the intervention phase.

3.2 Include complete citations or references.

Response:

Carr, K. A., Lin, H., Fletcher, K. D., & Epstein, L. H. (2014). Food reinforcement, dietary disinhibition and weight gain in nonobese adults. *Obesity* (Silver Spring), 22(1), 254-259. doi:10.1002/oby.20392

Cosgrove, K. P., Hunter, R. G., & Carroll, M. E. (2002). Wheel-running attenuates intravenous cocaine self-administration in rats: Sex differences. *Pharmacol Biochem Behav*, 73(3), 663-671. doi:10.1016/S0091-3057(02)00853-5

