appointments). These three appointments will be scheduled within 10 days of each other if possible, and at the same time of day to control for alertness, hunger cues, and mood. Before the laboratory visit, the parent will be asked to list one of his/her baby's favorite solid foods and rank the favorite food on a 7 point Likert-type scale. Only food that is ranked between 6 and 7 will be used as the test food. The parent will indicate during the initial screening if his/her infant has yet to try solid foods. The parent will be instructed to avoid feeding his/her child one hour prior to the visit and to provide the infant's favorite solid food for the food portion of the task. Upon arrival in the lab, the parent will be given a brief description of study protocols and will be asked to complete a consent form for his/her infant's participation. During the first visit, the infant will perform both computerized food and non-food tasks, sequentially, to allow the infant to become familiar with the lab setting and the game. During the second two appointments, the infant will perform the computerized food/non-food reinforcement task, one task each visit, and research staff will obtain anthropometric measures of both the parent and infant, and have the participating parent complete the reinforcing value of food and activities questionnaire and the Block food frequency questionnaire (FFQ), and Infant daily health Survey. The infant will qualify for the study if he/she has high relative food reinforcement (as described below). After baseline data collection, eligible families will be randomly assigned to the music program or play date control group. After the baseline data collection (0-m) laboratory visit of the Infant Toddler-Home Observational Measurement of Environment and randomization, participating families will attend laboratory assessments of infant and toddler food/non-food reinforcement task and anthropometrics, parental anthropometrics, dietary intake using Block FFQ and reinforcing value of food and activities questionnaire, as well as infant dietary intake phone interviews at 3-m, 6-m, 12-m, and 24-m. The IT-HOME will also be taken at 6-m, 12-m, and 24-m.

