The intervention and control programs are scheduled during the first year of the study (Intensive phase) for 37 weekly sessions structured into four semesters: Winter (10-week), Spring (10-week), Summer (7-week) and Fall (10-week). During the second year (maintenance phase) families will attend monthly sessions. Families will be run in groups of 10-12 families, with opportunities for makeup sessions.

The music program/intervention group will be the Music Together® program designed in collaboration with a local music studio, Betty's Music Together®. This program introduces infants to the pleasure of music making with their parents rather than passively receiving it from CDs or TV. This program provides a rich variety of music and playful activities, which will encourage infants and parents to participate at their own level in singing, moving, listening, or exploring musical instruments. Participating parents and infants will attend 45-minute classes as a group. Besides attending classes, parents will be encouraged to listen and sing

together with their infants at home during everyday home activities such as bath time, meal time, and bed time using the CD and instructional song book provided by the program. There are three enhancements to the usual Music Together® program that will be incorporated into treatment. First, to enhance practice during the first 3 months each family will be sent a text reminder every morning to engage in music at home, and parents are asked to respond every evening if they engage in home practice or not. This method was used in our pilot, and 85.4% of families in the music group and 84.8% in the play date group filled out the daily home practice surveys. Second, we will train parents to use music as a reinforcer for other behaviors, such that parents will be encouraged to play music and sing with their children when their children engage in good behaviors. This turns the tables on the usual parenting approach, to use food as a reward, which increases the value of food that could potentially lead to childhood obesity Third, families who completed the home practice surveys will be entered into monthly drawings during the intensive phase and bi-monthly during the maintenance phase for a \$50 gift card to a local grocery or coffee shop.

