Play date control. Using methods derived from our pilot study, the active control group will consist of 45-minute group play dates at the same intervals as the music group. Two research staff will be facilitating these play dates. Before the arrival of parents and children, different stations will be set up and the play date rooms will be child proofed. We will provide a variety of age-appropriate toys (excluding musical toys) for participating parents and infants to play with and enjoy. Parents will be encouraged to interact with other parents and children during the 45-minute play time. Research staff will be present at the play dates, but they will not interact with parents or children unless concerns or questions arise. Besides attending play dates, families will receive toys to play with at home. Parents will be told it is a way for them to spend time and bond with their children. Each family will be provided with two toys to play with at home each semester (8 different toys total) for the first year, and a total of two toys for the second year. Parents will be encouraged to play with their child at home during everyday home activities such as bath time, meal time, and bed time using the toy provided by the program as well as other toys the child has. As with the music group, for the first 3 months families will be provided text message reminders to play with their children using the play date toys, and will respond daily after completing playing, and families who completed the required home practice surveys will be entered each week into monthly drawings (during intensive phase) and bi-monthly (during maintenance phase) for a \$50 gift card to a local grocery or coffee shop.

During time of mandated social distancing, classes will become virtual for via Zoom for participants. This will involve participants meeting with their perspective groups for 30 minutes. The 30 minutes is a change from the typical 45 minutes because of having to be virtual and not being able

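### Both programmes are delivered in groups of 10-12 families, but the model in 18.1 and the 0.80 power in 18.2 assume, without saying so, that families sharing a group are independent

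*Combined protocol and SAP*

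**What the plan says.** Allocation is by family: "After baseline data collection, eligible families will be randomly assigned to the music program or play date control group" (10.1). Delivery is by group. Section 3.1 describes the intervention year as "comprised of 37 once per week group meetings of 10-12 infant-parent dyads", and 10.1 says "Families will be run in groups of 10-12 families, with opportunities for makeup sessions". The control is group-based too: "the active control group will consist of 45-minute group play dates at the same intervals as the music group" (10.1). The venues differ. Section 12.1 places the music classes in a music studio, and of the control it says "The play date intervention will take place in one of the lab rooms at the Behavioral Medicine Laboratory".

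Section 11.3 plans four cohorts of 20, 24, 24 and 24. Halved by arm, these give 10, 12, 12 and 12, which matches the stated group size. About one class per arm per cohort, or four per arm, is therefore a reasonable inference, but the protocol does not say it.

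The analysis in 18.1 is a mixed ANCOVA "which will include random intercepts and time effects clustered within participants", with arm, time and their interaction as fixed effects. Its reference to class variables means categorical factors, not music classes. There is no term for delivery group or cohort, and no sensitivity analysis for either. Section 18.2 derives 37 per arm for zWFL from an effect size of 0.667, alpha 0.05 and power 0.80, then adds 25% for attrition only. It mentions neither an ICC nor an independence assumption.

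**The concern.** Randomising individual families balances them at baseline. It does not prevent families who then share 37 weekly sessions and a year of monthly ones from becoming alike through a common leader, peers and atmosphere. If classes of the same arm diverge after baseline, each arm mean carries a class-level error averaged over only about four classes. A model with random effects for participants alone does not see that error. The standard errors of the 3, 6, 12 and 24-month group contrasts are then too small, and nominal 5% tests reject too often.

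The main problem is the understated standard error. The stated power is a second consequence, because a test that restores the 5% level has less than 0.80 at the planned size. zWFL matters most, being a primary outcome (2.1) and the one that sets the sample size (18.2).

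**Working it through.** **Inputs.** From 18.2: effect sizes 0.978 (FRR), 0.712 (pilot zWFL) and 0.667 (planning zWFL); alpha 0.05, taken as two-sided because that reproduces the figures; power 0.80; 37 per arm analysed and 46 randomised. From 11.3, by inference: four classes per arm. Assumed, because the documents give none: an ICC of 0.01, 0.05 or 0.10, meaning the share of the variance in change from baseline that lies between classes of the same arm. Each contrast is approximated by a two-sample comparison of changes.

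**The plan's own figures.** The independent two-sample t-test needs 18, 32 and 37 per arm for 0.978, 0.712 and 0.667, exactly as stated. Power for 0.667 is 0.808 at 37 and 0.886 at 46. No allowance for grouping is hidden in 37.

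**Formulas with clustering.**
- Mean class size at 37 per arm is 37/4 = 9.25, so the design effect is DE = 1 + 8.25 × ICC. If only the music arm is clustered, the arm-averaged value is (DE + 1)/2.
- The standard error is too small by 1 − 1/√DE.
- Type I error of the unadjusted test is about 2 × [1 − Φ(1.96/√DE)].
- Power of a test that holds 5% comes from a noncentral t with noncentrality 0.667 × √(37/(2·DE)). With DE = 1 this is 2.87; with both arms clustered it is 2.76, 2.41 and 2.12.

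| Class effect in | ICC | DE | SE too small by | Type I, formula | Type I, simulated | zWFL power, 72 df | zWFL power, 3 df |
|---|---|---|---|---|---|---|---|
| neither | 0 | 1.00 | 0% | 5.0% | – | 0.81 | 0.50 |
| both arms | 0.01 | 1.08 | 4% | 6.0% | 5.9% | 0.78 | 0.47 |
| both arms | 0.05 | 1.41 | 16% | 9.9% | 10.1% | 0.66 | 0.39 |
| both arms | 0.10 | 1.83 | 26% | 14.7% | 15.0% | 0.55 | 0.32 |
| music only | 0.01 | 1.04 | 2% | 5.5% | 5.5% | 0.79 | 0.49 |
| music only | 0.05 | 1.21 | 9% | 7.4% | 7.5% | 0.73 | 0.44 |
| music only | 0.10 | 1.41 | 16% | 9.9% | 9.9% | 0.66 | 0.39 |

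The simulation used 200,000 trials per case with classes of 9, 9, 9 and 10. The 3-df column is the level of information left when classes are paired by cohort.

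**All 46 retained** (DE = 1 + 10.5 × ICC). Both arms clustered: type I error 6.2%, 11.5%, 17.6% and power 0.85, 0.73, 0.60 (large-sample df). Music only: 5.7%, 8.2%, 11.3% and 0.87, 0.80, 0.73.

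**Tipping point at 37 per arm.** The critical t of 1.993 times √DE gives 2.07, 2.37 and 2.69. A primary p-value would thus have to be below 0.042, 0.021 or 0.009 (both arms) to stay significant at ICC 0.01, 0.05 or 0.10.

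**Which adjustment works.**
- A constant class intercept cancels from a change. With unit change variance per family, the contrast SE is √(2/37) = 0.232 with or without it.
- A post-baseline class variance of 0.05 gives √(2/37 + 2 × 0.05/4) = 0.281.
- An unrestricted class-by-time effect of the same variance also puts class variance at month 0, before classes exist, and gives √(2/37 + 4 × 0.05/4) = 0.323.
- Cohort matters as well. With no class effect and an assumed shared cohort variance share of 0.05 or 0.10, an unpaired t-test on class means (6 df) has simulated type I error of 2.6% or 1.6% and zWFL power of 0.53 or 0.43. Pairing by cohort holds 5%, with power of 0.52 to 0.54.

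**The case against.** **The size is assumed.** This is correct. At ICC 0.01 the effect is small, and the large figures need 0.05-0.10. Make-up sessions, home practice and individual outcome testing may dilute clustering. The control arm may have little of it, since play-date staff are present but "they will not interact with parents or children unless concerns or questions arise". That is why the music-only case is shown. Independence is nevertheless also an assumption about the ICC, and the plan leaves it unstated.

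**The structure is inferred.** This also stands. The protocol says of virtual sessions: "This will involve participants meeting with their perspective groups for 30 minutes". A reader might take that as proof that classes stayed intact online, but group may mean arm there. The inference rests on group size, venues and cohort sizes instead.

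**The planned test does not lose that power.** A reader might infer that the planned test has power of only 0.55-0.66. It does not. At effect size 0.667 and 37 per arm, the unadjusted t-test rejects in about 0.80, 0.77 and 0.75 of simulated trials at the three ICCs (both arms). Those rates are bought partly with inflated type I error, so the lower figures belong to a test that holds its level, which the plan does not run.

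**Eight classes are too few to adjust well.** This is the strongest point. A paired analysis has 3 df and power of about 0.5 even with no clustering, so its non-significance cannot overturn a primary result. This argues for a descriptive sensitivity analysis, not for silence.

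**Conclusion.** The concern holds in a conditional form. Sections 18.1 and 18.2 both assume zero post-baseline class variance without saying so. With four classes per arm and 37 analysed per arm, type I error is about 6%, 10% or 15% at ICC 0.01, 0.05 or 0.10 in both arms, with roughly half that excess if only the music arm is clustered. Level-holding zWFL power is about 0.78, 0.66 or 0.55 on large-sample df, and lower on class-level df. FRR at 0.978 keeps power of at least 0.87 on large-sample df, but at the same ICC its type I error is inflated just as much. Section 18.2 gives no effect size for the home environment score, so its power cannot be assessed.

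Three stronger readings are not supported. The documents do not show that clustering is present or large. They do not show that the sample must grow or that the primary model must be replaced; which analysis is primary remains the sponsor's judgement. Nor do cohort differences common to both arms bias the group contrast, because they cancel from it. They matter only for the error term of an adjusted analysis.

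**What to change.** 1. Store class as assigned (cohort by arm), regardless of where make-up sessions are attended.
2. In 18.1, keep the planned primary model and prespecify a sensitivity analysis of the post-baseline contrasts that accounts for both class and cohort. Use either cohort-by-time effects plus a random class coefficient on a post-baseline indicator (0 at month 0, 1 afterwards) with Kenward-Roger or Satterthwaite df, or a t-test on class-mean changes paired by cohort (3 df). Do not use an unpaired class-mean t-test, because shared cohort variance makes it conservative.
3. Because either analysis has very low df, also report the primary result over a stated ICC range, for example 0-0.10, dividing the primary t by the square root of the arm-averaged design effect. Present both checks descriptively, not as a pass/fail robustness rule.
4. In 18.2, state that 0.80 assumes independent families. Tabulate level-holding zWFL power for ICC 0-0.10 at 37 and 46 per arm, labelled as conditional on the assumed ICC.

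The cost is one stored variable, one extra analysis, wider sensitivity intervals and a less favourable stated power. No extra dyads are needed.
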